a The patient receiving double-blind study drug at dose level 2 has options to start with either the open-label LCZ696 100 mg b.i.d. (dose level 2) or LCZ696 50 mg b.i.d. (dose level 1) at the investigator's discretion.

Table 3-3 Safety monitoring criteria for up-titration at Visit 302 (Week 2 to 4)

Parameter	Visit 302 (Week 2 to 4)
Serum potassium level	$K \leq 5.4 \text{ mmol/L (mEq/L)}$ (local assessment)
Kidney function	$eGFR \geq 30 \text{ mL/min/1.73 m}^2$ $eGFR \text{ reduction} \leq 35\% \text{ compared to Visit 301}$ (local assessments)
Blood pressure	No symptomatic hypotension and $SBP \geq 95 \text{ mmHg}$.
AEs or conditions	No postural symptoms or any AEs that preclude continuation according to the investigator's judgment

OLE epoch initiation visit (Visit 301)

All patients must provide informed consent before any study-specific procedure for OLE epoch is performed. At Visit 301, patients' eligibility for entering the OLE epoch will be assessed by the investigator.

Patients will start the OLE epoch at this visit. This first visit of the OLE epoch will occur on the same day as the end of study (EOS) visit of the core part. Patients will be switched to an open-label LCZ696 at this visit. The patients receiving double-blind study drug at dose level 3 will start with open-label LCZ696 100 mg b.i.d. (dose level 2) ([Table 3-2](#)). The patients receiving double-blind study drug at dose level 2 will start with either open-label LCZ696 50 mg b.i.d. (dose level 1) or LCZ696 100 mg b.i.d. (dose level 2) at the investigator's discretion. The patients receiving double-blind study drug at dose level 1 will be also switched to an open-label LCZ696 but remain at same dose level (LCZ696 50 mg b.i.d.) up to Visit 302. Patients should continue to take their background medications for HF, with the exception of ACEIs or ARBs. The patients who have discontinued the double-blind study drug before this visit may be enrolled if eligible, however, should start with taking the LCZ696 50 mg b.i.d. (dose level 1).

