 - Female sterilization (have had surgical bilateral oophorectomy with or without hysterectomy) or tubal ligation at least 6 weeks before taking study treatment. In case of oophorectomy alone, only when the reproductive status of the woman has been confirmed by follow up hormone level assessment.
 - Male sterilization (at least 6 months prior to screening). For female subjects on the study, the vasectomized male partner should be the sole partner for that subject.

- Combination of any two of the following (a+b, a+c or b+c):
 - a. Use of oral, injected* or implanted* hormonal methods of contraception or other forms of hormonal contraception that have comparable efficacy (failure rate < 1%), for example hormone vaginal ring or transdermal hormone contraception*.
 - b. Placement of an intrauterine device (IUD) or intrauterine system (IUS)
 - c. Barrier methods of contraception: Condom or Occlusive cap (diaphragm or cervical/vault caps*) with spermicidal foam*/gel*/film*/cream*/vaginal suppository*

*: not approved in Japan, approved methods should be used.

In case of use of oral contraception women should have been stable on the same pill for a minimum of 3 months before taking study treatment.

Women are considered post-menopausal and not of child bearing potential if they have had 12 months of natural (spontaneous) amenorrhea with an appropriate clinical profile (e.g., age appropriate, history of vasomotor symptoms) or have had surgical bilateral oophorectomy (with or without hysterectomy) or tubal ligation at least 6 weeks ago. In the case of oophorectomy alone, only when the reproductive status of the woman has been confirmed by follow up hormone level assessment is she considered not of child bearing potential.

Patients fulfilling any of the following criteria at Visit 301, are not eligible for inclusion in the OLE epoch. No additional exclusions may be applied by the investigator.

26. Patients who discontinued study drug treatment during the core part due to an event or intercurrent illness. Eligibility can be re-considered if the event has resolved and no longer represents a risk to the patient and the patient can safely tolerate the administration of LCZ696 per the investigator's assessment.
27. Any medical condition that in the opinion of the investigator is likely to prevent the patient from safely tolerating LCZ696 or complying with the requirements of the study.

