28. Patients who have experience of angioedema event(s) which occurred and reported by the investigator during the core part of study.
29. Pregnant or nursing (lactating) women, where pregnancy is defined as the state of a female after conception and until the termination of gestation, confirmed by a positive hCG laboratory test.
30. Women of child-bearing potential, defined as all women physiologically capable of becoming pregnant, unless they are using highly effective methods of contraception while taking study treatment and for 7 days after stopping study treatment. Highly effective contraception methods include:
 - Total abstinence (when this is in line with the preferred and usual lifestyle of the subject. Periodic abstinence (e.g., calendar, ovulation, symptothermal, post-ovulation methods) and withdrawal are not acceptable methods of contraception
 - Female sterilization (have had surgical bilateral oophorectomy with or without hysterectomy), total hysterectomy or tubal ligation at least 6 weeks before taking study treatment. In case of oophorectomy alone, only when the reproductive status of the woman has been confirmed by follow up hormone level assessment.

- Male sterilization (at least 6 months prior to Visit 301). For female subjects on the study, the vasectomized male partner should be the sole partner for that subject.
- Use of oral, injected* or implanted* hormonal methods of contraception or placement of an intrauterine device (IUD) or intrauterine system (IUS), or other forms of hormonal contraception that have comparable efficacy (failure rate < 1%), for example hormone vaginal ring or transdermal hormone contraception*.

*: not approved in Japan, approved methods should be used.

In case of use of oral contraception women should have been stable on the same pill for a minimum of 3 months before taking study treatment.

Women are considered post-menopausal and not of child bearing potential if they have had 12 months of natural (spontaneous) amenorrhea with an appropriate clinical profile (e.g. , age appropriate history of vasomotor symptoms) or have had surgical bilateral oophorectomy (with or without hysterectomy), total hysterectomy, or tubal ligation at least 6 weeks ago. In the case of oophorectomy alone, only when the reproductive status of the woman has been confirmed by follow up hormone level assessment is she considered not of child bearing potential.

5 Treatment

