5.4 Treatment blinding

Single-blind LCZ696 will be dispensed to patients during the active treatment run-in epoch. During the active treatment run-in epoch, patients will receive LCZ696 and placebo to match enalapril. Patients, investigator staff, persons performing the assessments, and data analysts will remain blind to the identity of the treatment from the time of randomization until the core part database lock, using the following methods: (1) Randomization data are kept strictly confidential until the time of unblinding, and will not be accessible by anyone else involved in the study, and (2) the identity of the treatments will be concealed by the use of investigational treatment that are all identical in packaging, labeling, schedule of administration, appearance, and odor. A double-dummy design is used because the identity of the investigational treatment cannot be disguised, as the drug products are visibly different. Unblinding will only occur in the case of patient emergencies (see [Section 5.5.12](#)) and at the conclusion of the core part. [REDACTED]

In the OLE, the treatment will not be blinded to either the investigators or the patients.

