5.5.9 Discontinuation of study treatment

Patients may voluntarily discontinue study treatment for any reason at any time. The investigator should discontinue study treatment for a given patient if, on balance, he/she believes that continuation would be detrimental to the patient's well-being.

Study treatment discontinuation during the double-blind treatment epoch does not constitute withdrawal from the study, does not constitute withdrawal of consent and should not lead to the patient being withdrawn from the entire study unless the patient specifically withdraws his/her consent. Patients who have discontinued study drug are expected, and should be encouraged to, attend all the protocol specified study visits and perform all measurements as stipulated in the visit schedule ([Table 6-1](#)) and remain in follow up for the duration of the trial. If they fail to return for these assessments for unknown reasons, every effort (e.g., telephone, e-mail, letter) should be made to contact them as specified in [Section 5.5.11](#). The investigator must also contact the IRT to register the patient's discontinuation from study treatment.

During the OLE epoch, permanent discontinuation of LCZ696 constitutes withdrawal from the study. Under these circumstances, the patient should be evaluated at a final study visit (Visit 399). The investigator must also notify the IRT of the patient's discontinuation of LCZ696 and record it on the Drug Administration Record of the eCRF.

If the patient does not attend the study visits, follow-up should continue according to the specified schedule by telephone to determine if any AEs/endpoints pre-specified in the protocol have occurred, except in the case that the patient **specifically** refuses such follow-up and withdraws his/her consent.

The emergence of the following circumstances will require permanent investigational drug discontinuation:

- Withdrawal of informed consent
- Investigator thinks that continuation would be detrimental to the patient's well-being.
- Suspected occurrence of angioedema. A patient with any signs or symptoms of clinically significant angioedema should be thoroughly evaluated by the investigator.

The emergence of the following circumstances will require temporary or permanent discontinuation (study drug may be restarted once these circumstances no longer exist except the case of permanent discontinuation during the OLE epoch):

- Pregnancy and post-pregnancy during lactation period

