LIVER LABORATORY TRIGGERS	
• $3 \times \text{ULN} < \text{ALT} / \text{AST} \leq 5 \times \text{ULN}$• $1.5 \times \text{ULN} < \text{TBL} \leq 2 \times \text{ULN}$
LIVER EVENTS	
• $\text{ALT or AST} > 5 \times \text{ULN}$• $\text{ALP} > 2 \times \text{ULN}$ (in the absence of known bone pathology)• $\text{TBL} > 2 \times \text{ULN}$ (in the absence of known Gilbert syndrome)• $\text{ALT or AST} > 3 \times \text{ULN}$ and $\text{INR} > 1.5$• Potential Hy's Law cases (defined as $\text{ALT or AST} > 3 \times \text{ULN}$ and $\text{TBL} > 2 \times \text{ULN}$ [mainly conjugated fraction] without notable increase in ALP to $> 2 \times \text{ULN}$)• Any clinical event of jaundice (or equivalent term)• $\text{ALT or AST} > 3 \times \text{ULN}$ accompanied by (general) malaise, fatigue, abdominal pain, nausea, or vomiting, or rash with eosinophilia• Any adverse event potentially indicative of a liver toxicity *

*These events cover the following: hepatic failure, fibrosis and cirrhosis, and other liver damage-related conditions; the non-infectious hepatitis; the benign, malignant and unspecified liver neoplasms

Table 14-2 Follow Up Requirements for Liver Events and Laboratory Triggers

Criteria	Actions required	Follow-up monitoring
Potential Hy's Law case ^a	
 Discontinue the study drug immediately Hospitalize, if clinically appropriate Establish causality Complete liver CRF 	ALT, AST, TBL, Alb, PT/INR, ALP and γGT until resolution ^c (frequency at investigator discretion)
ALT or AST		
> 8 × ULN	
 Discontinue the study drug immediately Hospitalize if clinically appropriate Establish causality Complete liver CRF 	ALT, AST, TBL, Alb, PT/INR, ALP and γGT until resolution ^c (frequency at investigator discretion)
> 3 × ULN and INR > 1.5	
 Discontinue the study drug immediately Hospitalize, if clinically appropriate Establish causality Complete liver CRF 	ALT, AST, TBL, Alb, PT/INR, ALP and γGT until resolution ^c (frequency at investigator discretion)
> 5 to ≤ 8 × ULN	
 Repeat LFT within 48 hours If elevation persists, continue follow-up monitoring If elevation persists for more than 2 weeks, discontinue the study drug Establish causality Complete liver CRF 	ALT, AST, TBL, Alb, PT/INR, ALP and γGT until resolution ^c (frequency at investigator discretion)

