> 3 × ULN accompanied by symptoms ^b	
 Discontinue the study drug immediately Hospitalize if clinically appropriate Establish causality Complete liver CRF 	ALT, AST, TBL, Alb, PT/INR, ALP and γGT until resolution ^c (frequency at investigator discretion)
> 3 to ≤ 5 × ULN (patient is asymptomatic)	
 Repeat LFT within the next week If elevation is confirmed, initiate close observation of the patient 	
Investigator discretion
 
Monitor LFT within 1 to 4 weeks

ALP (isolated)		
> 2 × ULN (in the absence of known bone pathology)	
 Repeat LFT within 48 hours If elevation persists, establish causality Complete liver CRF 	
Investigator discretion
 
Monitor LFT within 1 to 4 weeks or at next visit

TBL (isolated)		
> 2 × ULN (in the absence of known Gilbert syndrome)	
 Repeat LFT within 48 hours If elevation persists, discontinue the study drug immediately Hospitalize if clinically appropriate Establish causality 	
ALT, AST, TBL, Alb, PT/INR, ALP and γGT until resolution^c (frequency at investigator discretion)
 
Test for hemolysis (e.g., reticulocytes, haptoglobin, unconjugated [Indirect] bilirubin)

Criteria	Actions required	Follow-up monitoring
	
 • Complete liver CRF 	
> 1.5 to \leq 2 \times ULN (patient is asymptomatic)	
 • Repeat LFT within the next week • If elevation is confirmed, initiate close observation of the patient 	Investigator discretion Monitor LFT within 1 to 4 weeks or at next visit
Jaundice	
 • Discontinue the study drug immediately • Hospitalize the patient • Establish causality • Complete liver CRF 	ALT, AST, TBL, Alb, PT/INR, ALP and γ GT until resolution ^c (frequency at investigator discretion)
Any AE potentially indicative of a liver toxicity*	
 • Consider study drug interruption or discontinuation • Hospitalization if clinically appropriate • Establish causality • Complete liver CRF 	Investigator discretion

*These events cover the following: hepatic failure, fibrosis and cirrhosis, and other liver damage-related conditions; the non-infectious hepatitis; the benign, malignant and unspecified liver neoplasms

^aElevated ALT/AST > 3 \times ULN and TBL > 2 \times ULN but without notable increase in ALP to > 2 \times ULN

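### OLE criterion 26 lets a patient restart on LCZ696 after a severe liver stop on the investigator's assessment alone, with no scheduled post-dose liver test before Month 4

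*Protocol*

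**What the plan says.** **Entry rule.** Section 4.2, criterion 26, excludes patients who stopped core study drug because of an event or intercurrent illness. It then provides that "Eligibility can be re-considered if the event has resolved and no longer represents a risk to the patient", and that the patient must be able to tolerate LCZ696 safely in the investigator's assessment. Inclusion criterion 8 and exclusion criterion 27 also rest on the investigator's judgement. Section 3.1.1.4 foresees such entrants: "The patients who have discontinued the double-blind study drug before this visit may be enrolled if eligible", starting at 50 mg b.i.d.

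**Liver stops.** Several rows of Appendix 2, Table 14-2, instruct the site to "Discontinue the study drug immediately". For isolated bilirubin above 2 x ULN the instruction is "If elevation persists, discontinue the study drug immediately". Neither the table nor Section 7.3 says whether drug may be given again.

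**Other safety stops.** Section 5.5.9 introduces a short list with "The emergence of the following circumstances will require permanent investigational drug discontinuation". It names withdrawal of consent, the investigator's view that continuing would be harmful, and suspected angioedema, but no liver event. Criterion 28 excludes "Patients who have experience of angioedema event(s) which occurred and reported by the investigator during the core part of study", with no route back. Appendix 3 allows no resumption after potassium of 6.0 mmol/L or more without case discussion with, and permission from, the sponsor's medical monitor.

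**OLE testing.** Under Table 6-2 and Section 6.5.4, the complete panel is taken at Visits 301, 304, 306 and 399. Visits 302 and 303 have only potassium, BUN and creatinine, plus local potassium and eGFR at Visits 301 and 302.

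**The concern.** A potential Hy's Law case is among the most serious hepatic findings a trial can record, and Table 14-2 treats it so. The usual consequence is that drug is not given again unless another cause has been established and someone beyond the site has agreed. Here the rule on re-exposure has to be inferred from a general criterion that was not written for liver events. That criterion requires neither a second opinion, nor a liver result in hand, nor early liver tests afterwards.

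What is at stake is the safety of individual patients in the OLE. The core efficacy comparison is not affected by OLE entry.

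**Working it through.** The documents give no figure to reproduce, so the check compares provisions and counts scheduled tests.

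**Step 1: which stops are immediate.** Table 14-2 has five outright: potential Hy's Law case; ALT/AST above 8 x ULN; above 3 x ULN with INR above 1.5; above 3 x ULN with symptoms; jaundice. Isolated bilirubin above 2 x ULN is a sixth if it persists. The row for above 5 to 8 x ULN stops drug only after more than two weeks and is not counted. The first, second, third and fifth of these form the severe group.

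**Step 2: does any rule close the route back?**

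| Event in core part | Rule on giving drug again |
|---|---|
| Angioedema | Permanent stop (5.5.9); OLE bar (criterion 28) |
| Potassium 6.0 mmol/L or more | Medical-monitor permission (Appendix 3) |
| Severe liver stop | None stated; criterion 26 applies |

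Of the five OLE exclusions (26 to 30), none names a liver event. The hepatic exclusion in criterion 22 belongs to the core part. The restart text in Section 5.5.5 cites Appendices 3, 4 and 5 but not Appendix 2, so the core part has the same gap.

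**Step 3: what counts as resolved.** Criterion 26 does not define the word. The only definition for liver events is footnote c of Table 14-2. Besides return to baseline, it accepts stable values at three monitoring visits and values still elevated after six months. If a site borrows that definition, a patient with persistently abnormal tests can count as resolved. The separate condition that the event is no longer a risk still applies, but the investigator judges that too.

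**Step 4: scheduled liver tests after dosing starts.**
- Core part: Visit 203 (Week 4) and Visit 204 (Week 8), so 2 by Week 8.
- OLE: none at Visits 302 and 303, so 0 by Week 8. The first is Visit 304 at Month 4.
- Month 4 in weeks, taking 30.44 days per month: 4 x 30.44 / 7 = 17.4.
- Section 3.1.1.4 aims for 200 mg b.i.d. by Week 8. If that is met, time at target dose before the first test is 17.4 - 8 = 9.4 weeks.
- Dose range over that time: 200 / 50 = 4-fold, in two steps.

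**Step 5: the pre-dose panel.** The Visit 301 panel goes to the central laboratory, and the first dose is taken the next day. Section 3.1.1.1 says of screening that laboratory results can take several days. Nothing requires the liver result to be seen before dosing, and the up-titration criteria in Table 3-3 include no liver test.

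**The case against.** The case on the other side is substantial.

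- **The default is exclusion.** Re-entry needs three conditions together: resolved, no longer a risk, and LCZ696 safely tolerable. An injury attributed to LCZ696 would not readily meet the last two.
- **The investigator is informed.** The severe rows require causality to be established and a liver CRF, with follow-up until resolution. Section 7.3 requires alternative causes to be excluded. Section 6.5.4 requires follow-up after a laboratory-driven stop and lets the medical monitor ask for tests. SAEs reach the sponsor within 24 hours. Patients off drug are expected to keep attending core visits, so off-drug panels will usually exist before Visit 301.
- **Some stops will have occurred on enalapril.** Every entrant also completed the LCZ696 50 mg run-in, with a complete panel at Visit 199.
- **The comparators differ.** Section 6.5.8 gives a mechanism for angioedema, and Section 5.5.5 names hyperkalemia as a dose-adjustment focus. The protocol describes no hepatic signal for LCZ696.
- **Optional safeguards exist.** Unscheduled panels, slower titration and the adverse-event line in Table 3-3 are all available.

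All of this stands as mitigation. None of it requires a liver test or a second decision before re-exposure. The enalapril point helps little at Visit 301, because site staff "will remain blind to the identity of the treatment from the time of randomization until the core part database lock", unless the code was broken or the event was unblinded as a SUSAR.

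A reader might infer more: that the sentence "No additional exclusions may be applied by the investigator" forces the investigator to accept such patients, or that re-exposure happens with nobody at the sponsor aware. The documents support neither. Criterion 27 lets the investigator refuse on medical grounds, and the sponsor receives the SAE reports and central laboratory results. Nor do they support an absolute bar over all six rows. One row turns on symptoms such as fatigue or nausea, which Table 7-1 lists as common in this population.

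**Conclusion.** The point holds in this form: after a severe liver stop, the protocol informs the decision to re-expose but does not gate it, and then schedules no post-dose liver test for about 17 weeks. That is less protection than the protocol gives after angioedema or severe hyperkalemia. The DMC covers only the core part (Section 8.4), so it does not fill the gap.

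The number affected cannot be estimated, because the documents give no rate of liver stops. About 180 patients are expected to complete the core part, and re-entrants of this kind will be very few. The case for a change rests on the severity of the harm and the low cost of preventing it.

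The 9-week figure assumes that target dose is reached by Week 8; a slower titration shortens it. The concern about lasting elevation assumes that a site reads criterion 26 with the Table 14-2 footnote. The lack of a gate and the 17-week interval depend on neither assumption.

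**What to change.** 1. Add to criterion 26, and to Appendix 2 with a cross-reference in the Section 5.5.5 restart text, a rule for four stops: potential Hy's Law case, ALT/AST above 8 x ULN, above 3 x ULN with INR above 1.5, and jaundice. After any of these, study drug or LCZ696 may be given again only if:
   - a cause other than study drug is documented;
   - liver tests are back to baseline or clinically acceptable, on a result seen before the first dose;
   - the sponsor's medical monitor has given permission, using the existing Appendix 3 condition.
2. For any patient stopped under any of the six immediate-stop liver rows who re-enters, add ALT, AST and bilirubin to the blood already drawn at Visits 302 and 303.

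The cost is a few sentences of protocol text, extra analytes at two visits for a handful of patients, and a short delay before dosing while the result is awaited. A very few patients may lose OLE access.
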